#### Postoperative strategy:

- o Pain control using balanced analgesia
- o Gum chewing
- o Antithrombotic prophylaxis by low-molecular-weight heparin (40mg/60mg, depending on patient weight, 6 hours post-op during entire hospital stay)
- Early oral refeeding (as of 4 h postoperative)
- Rapid mobilization (as of 4 h postoperative)
- Venflon removal 6 hours post-op
- o Standard criteria for hospital discharge the day after surgery, checked by a physician:
  - Lack of organ dysfunction (evaluated by physical examination)
  - > Afebrile condition
  - Simple effective analgesia
  - Normal feeding
  - Independent mobility
  - Patient consent
- o Planned outpatient follow-up: stitches/ skin staples removal on day 7, postoperative checkup on day 30
- o Home care if needed

The protocol will have to be well-known by surgeons, anaesthetists and the nursing team.

# 2) «Conventional setting» protocol

#### Pre-hospital assessment

o Surgical indication determination and surgical procedure explanation

#### Preoperative strategy:

- Hospitalization on surgery day
- o Fasting as of midnight prior to the day of surgery

### Perioperative strategy:

Treatments according to the surgeons and the anaesthesiologists practice:

- o Anti-infectious prophylaxis: Cefazolin 2g IV
- o Balanced anaesthesia via halogens gases

#### Postoperative strategy:

- Mobilization depending on patient's general condition, on the evening of the surgery, at minimum 6 hours post operation
- Antithrombotic prophylaxis by low-molecular-weight heparin (40mg/60mg, depending on patient weight, 6 hours post-op during entire hospital stay)
- Same day refeeding, depending on the patient's general condition and according to her desire, proposed on the evening of the surgery at minimum 6 hours post operation
- o Bladder catheter and Venflon removal on day 1
- o Standard criteria for hospital discharge the day after surgery, checked by a physician:
  - ➤ Lack of organ dysfunction (evaluated by physical examination)
  - > Afebrile condition
  - > Simple effective analgesia
  - Normal feeding
  - Independent mobility
  - Patient consent
- Planned outpatient follow-up: stitches/ skin staples removal on day 7, postoperative checkup on day 30
- o Home care if needed

#### • Issues:

#### o Main:

> Total costs: hospitalization costs and costs during the first month after surgery (ambulatory, home care and family/friends loss of earnings) (1)

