**Intervention:** 

Two types of perioperative settings will be compared:

o Group 1: "Fast track" protocol

Group 2: conventional setting

1) "FAST TRACK" protocol

Preoperative evaluation and information:

o Patient information of the study during the pre-hospitalisation visit and patient consent to

participate in the study prior to hospitalization.

o Patient general health state optimization proposal prior to hospitalization:

Smoking cessation, if necessary (specialized consultation)

Weight loss, if necessary (nutrition consultation)

Patient autonomy and social environment evaluation (home care proposal if

necessary)

7

« Fast track » surgery on patient undergoing minimally invasive gynaecologic procedure : a randomized clinical trial. V2.0 – 2015.09.29

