#### Sample size

Sample size is calculated based on the difference of means for total costs in between the two groups including hospitalization costs and costs during the first month after surgery (ambulatory, home care and social environments loss of earnings). The null hypothesis tested will be that costs are identical in the two groups.

In order to obtain a power of 90% for type I error with a significance threshold at 0.05 in a two-tailed distribution and in order to highlight a difference equal to 0.5 standard deviations which is clinically relevant, the study will need to include 170 patients (n1 = 85; n2 = 85). Assuming an average cost of CHF 10'000 per hysterectomy for benign indication (CHF 12'809 in 2013, information given by [name], financial medical controller), it will be possible to highlight a statistically significant difference of CHF 1400 per surgery corresponding to 10% of the total amount which would be considered as clinically relevant.

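### The main cost outcome omits pre-admission services listed only for the Fast track arm, so any extra use there would overstate the saving

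*Combined protocol and SAP*

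**What the plan says.** Under Issues, Main, the primary outcome is "Total costs: hospitalization costs and costs during the first month after surgery (ambulatory, home care and family/friends loss of earnings"). The Sample size section uses the same window: "including hospitalization costs and costs during the first month after surgery (ambulatory, home care and social environments loss of earnings"). In both places ambulatory cost belongs to the month after surgery.

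Under Intervention, the Fast track protocol includes a "Patient general health state optimization proposal prior to hospitalization", with these items:

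- "Smoking cessation, if necessary (specialized consultation")
- "Weight loss, if necessary (nutrition consultation")
- "Patient autonomy and social environment evaluation"

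For the conventional arm, the Pre-hospital assessment has one entry: "Surgical indication determination and surgical procedure explanation".

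Four other places bear on the point:

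- Recruitment: each patient learns her allocation at once, so that her perioperative planning can be prepared.
- Preoperative strategy, both arms: admission is on the day of surgery.
- Instruments: hospital and ambulatory costs come from an extract by patient number (EDS), with no start date stated. Home care is costed from invoices.
- Ethics: steps of the Fast track protocol are already used case by case in conventional care.

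**The concern.** The stated objective is to judge the Fast track concept on cost and satisfaction, and the rationale speaks of a financial benefit for public health. The description of the concept in the Introduction counts a preoperative part among its four components. The cost window nevertheless opens at admission, after part of the programme under test may already have been delivered and paid for.

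Because allocation is disclosed immediately, the pre-admission services can follow randomization and so can differ between arms as a result of it. If they do, the estimated saving is too large, in the direction of the trial's hypothesis. Intention-to-treat analysis does not help, because the cost is never counted. As written, the trial also could not show that the omission is negligible: adherence is to be evaluated in the Fast track group only, and nothing provides for costing these services.

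**Working it through.** **1. Does the definition exclude these services?** A consultation on a day before admission is not a hospitalization cost, and it is not a cost of the month after surgery. Taken literally, both statements of the outcome exclude it.

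**2. The plan's own sample size.** Inputs from the Sample size section: difference 0.5 SD, two-sided alpha 0.05, power 90%.

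- n per group = 2 × (1.960 + 1.282)² / 0.5² = 84.1, rounded up to 85, so 170 in total. This reproduces the stated figure.
- The t-test power at 85 per group is 0.900.

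The point raised here does not affect this figure.

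**3. Precision implied by the plan.**

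- The plan equates CHF 1400 with 0.5 SD, so SD = 1400 / 0.5 = CHF 2800.
- SE of the difference = 2800 × √(2/85) = CHF 429.5.
- 95% CI half-width = t(0.975, 168 df) × 429.5 = CHF 848.

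**4. Size of the omission.** Net omission per patient: B = (uptake in Fast track − uptake in control) × price per user. The documents give none of these inputs, so the values below are assumptions for illustration. They take a 10-point difference (for example 30% v 20%) or a 20-point difference (40% v 20%), at CHF 300, 600 or 1000 per user.

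**5. Effect on the conclusion.** Suppose costs counted from randomization are truly equal. The t statistic on the plan's outcome then follows a noncentral t distribution with 168 df and noncentrality B / 429.5 (for B = 200, 0.466).

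| Difference in uptake × price | B (CHF) | Share of 1400 | Two-sided rejection | Tail showing a Fast track saving |
|---|---|---|---|---|
| none | 0 | 0% | 5.0% | 2.5% |
| 0.1 × 300 | 30 | 2.1% | 5.1% | 2.9% |
| 0.1 × 600 or 0.2 × 300 | 60 | 4.3% | 5.2% | 3.4% |
| 0.1 × 1000 | 100 | 7.1% | 5.6% | 4.2% |
| 0.2 × 600 | 120 | 8.6% | 5.9% | 4.6% |
| 0.2 × 1000 | 200 | 14.3% | 7.5% | 6.7% |

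Against the CI half-width, 60/848 = 7% and 200/848 = 24%.

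**6. Sensitivity.** With an assumed SD of CHF 4000 (SE 613.6), the two-sided rates for B = 60, 120 and 200 are 5.1%, 5.4% and 6.2%. With SD 2800, the two-sided rate reaches 10% only at B of about CHF 282, above every scenario in the table.

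These are not type I error rates for the plan's own null hypothesis, which concerns costs as the plan defines them and stays at 5%. They describe how often the trial would declare a difference when costs from randomization are equal.

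**The case against.** The strongest objection is that no difference between arms is shown. The two consultations are offered only where needed, and the Ethics section says that conventional care already uses Fast track steps case by case. The one-line control entry is not a complete list either: it omits study information and consent, which the Fast track list contains ("Patient information of the study during the pre-hospitalisation visit and patient consent to" and so on) although Recruitment gives them to every patient. This stands. The bias is conditional and may be zero.

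Second, the prices are unanchored. At CHF 100 per user, a difference of 10 to 20 points omits only CHF 10 to 20, or 0.7% to 1.4% of CHF 1400. This also stands; the documents do not show that the amount is material.

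Third, an episode cost from admission is a legitimate choice, applied identically in both arms. That is true of the plan's null hypothesis. It does not fit the stated aim, which is what the Fast track concept costs.

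Fourth, existing tools may capture some of this. The extract has no start date and may hold hospital-billed visits, and the case report form follows the clinical pathway. But the outcome definition would still not count those visits, and the text does not say that these consultations are itemised. Home care in the month after surgery is already counted, so only the autonomy and social evaluation itself, if billed, is at issue.

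Fifth, it would be lighter to keep the outcome and add a sensitivity analysis. That would leave the primary estimate without part of the intervention's own cost.

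**Conclusion.** The concern holds. It is a gap in the definition of the main outcome, and it should be fixed. If Fast track patients use the listed services more than controls, the direction is known: the saving is overstated. The size is unknown. It is CHF 0 with equal uptake and, under the assumed inputs, CHF 30 to 200 per patient. That would not overturn a true saving near CHF 1400, but it could tip a borderline result. Confidence is medium, because both the difference in use and the prices are assumptions and the SD of CHF 2800 is only implied by the plan.

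**What to change.** - Start the cost window and the EDS extract at randomization in both arms.
- Before admission, count a pre-specified list (smoking-cessation consultation, nutrition consultation, autonomy and social evaluation), whichever arm uses them.
- Record their use in both arms on the existing case report form and care maps, and report uptake by arm.
- Apply an invoice or a unit cost where the extract does not cover a service.
- Keep the present window as a sensitivity analysis.

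The cost is one changed definition, one start date, a few form items, and invoices or unit costs for services billed outside the hospital (the plan now uses invoices only for home care). The fixed list avoids case-by-case judgement about which visits count, but other pre-admission costs, such as earnings lost before admission, stay outside it. The estimated saving may be slightly smaller. No patient's care changes and the sample size stays at 170.

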#### Secondary:

- Patient satisfaction (2)
- ➤ Earlier rehabilitation (3): pain comparison via pain scale (0-10) and resumption of normal bowel function via day of first stools and gas post-op
- Morbidity during the first post-operation month (4):
  - -readmission rate
  - -number of infections
  - -number of thromboembolic events

In order to measure the impact of the intervention on our practice, the length of hospitalization "Fast track" and conventional setting will be compared.

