**Methods:** 

Design:

Randomized control trial: the randomization in two groups will be performed by computer using

block of different sizes (2 and 4) before patient inclusion. Sealed, opaque and numbered

envelopes will be prepared and patients will be included consecutively.

Population:

All patients in our gynaecology department, in whom an indication of total or subtotal

laparoscopic hysterectomy for benign indication with or without adnexectomy has been

established (including robot-assisted interventions), will be proposed this study.

Exclusion criteria:

Patients needing an additional surgical procedure such as a prolapse surgery or urinary

incontinence surgery as well as malignant pathologies will not be included in the study due to

prolonged operative time which could compromise early home return. Non-French speaking

patients will also be excluded from the study due to the necessity of their collaboration in filling a

logbook drawn up in French on a daily basis during their hospitalization.

6

Etude CCER n° 15-103 : Fast Track\_V.2.0-2015.09.29

« Fast track » surgery on patient undergoing minimally invasive gynaecologic procedure: a randomized clinical trial. V2.0 – 2015.09.29

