**Recruitment:** 

During pre-hospitalisation visit where surgical indications are established, eligible patients will

meet a research nurse who will explain the study giving patients oral and written information. If

the patient agrees to participate in the study, she will be included randomly in one of the two

groups after having signed a consent form. She will immediately be informed of her allocation to

the "Fast track" or the control group in order to best prepare her personal perioperative planning.

To increase the number of patients recruited, patients that meet the criteria of the study but who

were not informed during the pre-hospitalisation visit will be contacted by a research nurse after

the weekly colloquium of surgical indications, colloquium where all surgical indications of the

department of gynaecology of the HUG are confirmed.

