#### • Instruments:

- 1) Costs of the two types of setting ("Fast track" and classic) will be compared taking into account hospitalization and ambulatory costs which will be obtained via the patient EDS number as discussed with the medico-information department ([name]). In addition, home care will be accounted for via invoices and family/friends loss of earnings will be calculated based on the number of absent working days. With Switzerland's median wage of CHF 6118 per month in 2012 and approximately 21 working days per month, we can estimate a median wage of CHF 291 per working day.
- 2) Patients satisfaction in both groups will be evaluated via a satisfaction questionnaire on their day of return home and at their follow-up visit one month after surgery.
- 3) Patients will be given a logbook questioning them on their pain awareness, their digestion and their mobilisation during their hospital stay.
- 4) Morbidity during the first month post-operation (i.e. readmission rate, number of infections and number of thromboembolic events) will be evaluated via the medical staff case report form.

A medical staff case report form containing their detailed clinical pathway will be used to verify patient's adhesion rate at each stage of the protocol.

A care map for each group will be used by the medical staff as a synopsis of the clinical pathway and will have to be signed by each medical intervener (nurse, gynaecologist and anaesthetist).

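### Bowel recovery is scored by an undefined day although the arms' care timings differ by hours, which costs power on a secondary outcome

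*Combined protocol and SAP*

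**What the plan says.** Issues, Secondary lists pain scores and "resumption of normal bowel function via day of first stools and gas post-op" as the measures of earlier rehabilitation. No section says whether a day is a calendar day or a 24-hour period from surgery.

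The data come from the patient. Instruments, item 3, states: "Patients will be given a logbook questioning them on their pain awareness, their digestion and their mobilisation during their hospital stay". Exclusion criteria describes a "logbook drawn up in French on a daily basis during their hospitalization". No section asks for a clock time of first gas, first stool or end of surgery for this outcome.

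The care contrast is written in hours. The Fast track postoperative strategy has "Early oral refeeding (as of 4 h postoperative") and "Rapid mobilization (as of 4 h postoperative"). In the conventional arm refeeding is "proposed on the evening of the surgery at minimum 6 hours post operation", and mobilization has the same 6-hour minimum. Both arms carry the same rule: "Standard criteria for hospital discharge the day after surgery, checked by a physician".

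Sample size powers the trial on total cost only. Type of analysis names no test for bowel function.

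**The concern.** The smallest documented difference in the start of refeeding and mobilization is 2 h, while the response is read to the nearest day. If the effect on bowel recovery is also a matter of hours, most patients in both arms fall into the same one or two categories and a real gain may be missed. Because discharge is assessed the day after surgery, an in-hospital logbook may cover only days 0 and 1, which reduces the number of values further.

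At stake is one secondary measure of the benefit that the programme is meant to deliver. A null result on days could be read as no gain in bowel recovery when the scale was too coarse to show one. Clock times not recorded prospectively cannot be reliably recovered later.

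**Working it through.** **1. The plan's own figure.** Sample size gives 85 per arm for a 0.5 SD difference, two-sided 0.05, 90% power. Per arm, n = 2(1.960 + 1.282)² / 0.5² = 2 × 10.51 / 0.25 = 84.1, rounded up to 85. Power at 85 is 0.903 (0.900 with the t distribution). The figure reproduces, but it concerns cost. The documents give no mean, SD or expected gain for bowel recovery.

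**2. Unit against contrast.** The care timings differ by at least 6 − 4 = 2 h, and the outcome unit is 24 h. On a calendar-day reading the score also depends on when surgery ended. First gas 12 h after surgery falls on day 0 if surgery ended at 10:00 (10 + 12 = 22:00), but on day 1 if it ended at 14:00 (14 + 12 = 26, or 02:00 the next day).

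**3. Power by scale.** From the plan: 85 per arm. The two-sided 0.05 level is borrowed from the cost outcome. Assumed: log-normal time from end of surgery, surgery ending uniformly between 10:00 and 17:00, the means, SDs and gains below, a Fast track SD that shrinks in proportion to its mean, and a t-test. Calendar day is the integer part of (end-of-surgery clock time + hours to event)/24. The 24-hour period is the integer part of hours/24. There were 4,000 simulated trials per row, and a Wilcoxon test on 1,000 of them gave the same pattern.

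| Control mean (SD), h | True gain, h | Hours | Calendar day | 24-h period | Points lost (calendar / 24-h) |
|---|---|---|---|---|---|
| 18 (8) | 4 | 96% | 79% | 65% | 17 / 32 |
| 24 (10) | 4 | 81% | 55% | 65% | 26 / 16 |
| 36 (16) | 6 | 76% | 64% | 69% | 12 / 7 |
| 48 (20) | 6 | 54% | 49% | 49% | 6 / 5 |

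Points lost are taken before rounding. With a gain of 8 h at a mean of 18 or 24 h, almost nothing is lost on any scale.

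**4. Sensitivity to the SD model.** Taking means of 20–24 h, SDs of 8–10 h, a 4 h gain and a Mann-Whitney test, and varying how the Fast track SD is set, power is about 83–97% on hours, 54–85% on calendar days and 39–80% on 24-hour periods. The 81% in the table lies just below the first range because its SD shrinks with the mean. At mean 20 h, SD 8 h, the calendar-day loss is about 25 points with a shrinking SD (95% against 70%) but about 10 with equal SDs. At mean 24 h it is about 18–38 points. The direction is the same in all of these; the size is not.

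**5. Operating slot.** With no true difference and balanced slots, calendar-day scoring rejects in 5.0–5.7% of trials. If Fast track operations are assumed to end 2 h earlier on average, it rejects in 35%, 18%, 11–12% and 8–9% at means of 18, 24, 36 and 48 h. Hours and 24-hour periods from end of surgery stay at 4–5%.

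**6. End of the logbook.** Under the same assumptions 4%, 14%, 46% and 73% of control patients (means 18, 24, 36 and 48 h) have the event after day 1. For a patient discharged on day 1 it would go unrecorded. None of the power figures above includes this loss.

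**The case against.** **An earlier operating slot could pass for faster recovery.** A reader might infer this, since the patient is told at once whether she is in "the 'Fast track' or the control group in order to best prepare her personal perioperative planning", and slot is neither fixed nor adjusted for. The documents do not support it as a finding. Calendar day is not in the text. No section ties slot to arm. The planning mentioned is the patient's own, and both arms are admitted on the day of surgery. Randomization balances slots on average, and then the error rate stays near 5%. The rates in step 5 need both a calendar-day reading and an arm difference that was supplied as an assumption. What remains is an exposure that open allocation does not exclude.

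**The loss is modelled on favourable inputs.** This is partly right. Means of 20–24 h suit first gas; at 36–48 h, as may apply to stools, the loss is small. The SD model matters, as step 4 shows.

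**Patient-reported clock times are not exact.** This also stands. If events between 23:00 and 07:00 are reported on waking, with a 2 h reporting error (both assumed), hour-scale power falls from 97% to 90% at mean 20 h and from 86% to 78% at 24 h. That gives back 7 of the roughly 10–25 points at mean 20 h, SD 8 h, and 8 of the 18–38 points at 24 h. Hour-scale null rejection under a 2–3 h slot difference also rises, to about 10–14%, so hours reduce that exposure without removing it.

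**The outcome is minor.** It is secondary and carries no power claim, the logbook also covers mobilisation, and length of stay is compared separately. The logbook form is not in the text, so it may already ask for times. This limits the weight of the point but does not remove it, because the stated measure is the day.

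**Conclusion.** The point holds as a cheap improvement of minor weight. Scoring bowel recovery by day, against care timings set in hours, loses power under either reading of the word. The loss is largest for an event expected within about a day, such as first gas: calendar-day scoring cost about 10 to 38 points in the scenarios with means of 20–24 h and a 4 h gain. It is about 3–7 points at a mean near 48 h and close to nil if the true gain is large. Every bowel-time input is assumed, including the gain itself; the documents state a difference in care timing, not in bowel recovery. A bias from operating slot is conditional on a calendar-day reading and on slots that differ by arm, and the documents show neither.

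**What to change.** In Issues, Secondary, replace the day of first stools and gas with the time in hours from end of surgery to first gas and, separately, to first stool. In Instruments, have the logbook ask for the date and clock time of each event, and add the clock time of end of surgery to the medical staff case report form. In Type of analysis, name a time-to-event comparison that treats events not seen by the end of the logbook as censored. If days are kept, define the day and report end-of-surgery times by arm.

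The cost is a few fields on forms that already exist, plus some error in patient-reported times, mainly overnight. Care and sample size do not change. Clock times do not recover events after the logbook ends; censoring only handles them openly. Since discharge may itself depend on recovery, the number censored should be reported by arm.
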